7.6 Exploratory Analyses

Exploratory analyses may include, but are not limited to:

1. The 5 remaining items from the IOI-CHI as well as a composite score created by computing the mean across all 6 items.
2. The 2 remaining items from the COSI as well as a composite score created by computing the mean across all 3 items.
3. Telehealth acceptance as assessed by an interviewer-administered scale that consists of 5 items in which participants rate the ease of use or utility of telehealth equipment using a 5-point Likert scale. A higher score indicates a more favorable rating. Each item will be examined separately before being analyzed collectively as part of a composite score created by computing the mean across all 5 items.
4. Subgroup analyses of the primary and secondary outcomes including but not limited to sex, race, and education. Interactions between treatment assignment and subgroups will be tested relative to $p < 0.10$.
5. The effect of treatment assignment on the total number of contacts between the provider and participant. The total number of provider-participant contacts is quantified by the study audiologists using forms completed at every encounter. In a supplemental analysis, the number of contacts will be examined across specific modalities including face-to-face contact in a clinic, face-to-face contact outside of a clinic (e.g. home visits), and remote contact (e.g. video calls, phone calls, etc.)
6. The effect of treatment assignment on the total time spent between provider and participant. The total number of minutes during which the provider and participant interacted is quantified by the study audiologists using forms completed at every encounter. In a supplemental analysis, the number of minutes will be examined across specific modalities including face-to-face contact in a clinic, face-to-face contact outside of a clinic, and remote contact.
7. Estimating the linear and potentially nonlinear dose-response relationship between utilization of hearing services and hours of hearing aid use at one-year post-randomization. This will include testing the total number of contacts between the provider and participant, the total amount of time the provider and the participant spend interacting, and differences by modalities such as face-to-face contact in a clinic, face-to-face contact outside of a clinic, and remote contact.
8. Using mixed effects models to examine trends over time from randomization to the two-year follow-up assessment. Time will be defined categorically or continuously with a time spline specified at 12 months. An interaction between treatment assignment and time will be included in the model to estimate the effect of participants in the conventional HHC treatment arm gaining access to telehealth services one-year post-randomization.

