Objectives	Primary: 1. To compare the effect of the telehealth hearing health care (HHC) versus conventional HHC delivery models on hours of hearing aid use (primary outcome) at 1-year post-randomization. Secondary: 2. To compare the effect of the telehealth HHC versus the conventional HHC delivery model on patient-centered hearing and communication outcomes, social functioning, and quality of life at 1-year post-randomization. 3. To compare utilization of hearing services required by each HHC delivery model. 4. To evaluate the association of the telehealth HHC intervention with changes in hearing aid use and patient-centered hearing and communication, social functioning, and quality of life measures from baseline to up to two years post-intervention.
Outcomes	Primary: Average daily hours of hearing aid use at 1 year, as measured through objective hearing aid data logging. If a participant wears a hearing aid in both ears, then the ear with the greatest number of hours logged will be selected. Key secondary: • Treatment satisfaction, as assessed by a single item from the International Outcome Inventory – Comprehensive Hearing Intervention (IOI-CHI) • Ability to hear for the primary communication goal, as assessed by a single item from the Client-Oriented Scale of Improvement (COSI) goals achievement questionnaire • Hearing-specific quality of life, as assessed by the Hearing Handicap Inventory for the Elderly Screening Version (HHIE-S) questionnaire

Randomization and stratification	1:1 random block randomization, stratified by degree of hearing loss (mild vs. moderate or greater), cohort (originally recruited to the ACHIEVE study from the Atherosclerosis Risk in Communities Study [ARIC] or de novo from the community), and field center to achieve balance among these factors between treatment arms. Similar to ACHIEVE, spouse pairs will be randomized to the same treatment group.					
Study Interventions	Conventional HHC: Participants randomized to continued conventional HHC group will, for the first year of this study, continue to receive the same conventional, clinic-based hearing intervention received in the original ACHIEVE study, with clinic-based visits every 6 months to reinforce self-management strategies and perform hearing aid checks. In year two, participants randomized to continued conventional HHC will crossover to receive telehealth HHC.					

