·	Telehealth HHC: The telehealth HHC intervention allows for remote access to hearing health care services and continuous support of participants' hearing loss needs via telehealth in addition to conventional clinic-based hearing booster sessions that occur every 6 months. Participants randomized to the telehealth HHC group will receive telehealth HHC for both years of the study.					
Participant Duration	2 years, with data collection follow-up visits occurring every 6 months					
Study Duration	5 years					
Statistical Methodology	Primary: The primary analysis compares hearing aid utilization between groups randomized to telehealth HHC versus conventional HHC delivery model under the intention-to-treat paradigm, analyzing individuals according to their random allocation, irrespective of the treatment received. Consistent with best practices in clinical trials, we will assess the comparability of the randomized groups with respect to known confounders (e.g., recruitment source, site, level of hearing impairment, Quick Speech in Noise score, self-reported acceptance of telehealth at baseline, self-reported and objectively measured baseline hours of hearing aid use, self-reported baseline hours of hearing assistive technologies use, the number of days hearing log data was measured prior to randomization, and the number of visits prior to randomization at which a participant provided hearing logging data). These variables will be considered as covariates in all models. We will use a weighted regression model with an identity link to compare average daily hours of hearing aid use at 1-year post-randomization between participants assigned to the telehealth HHC and conventional HHC. To account for the non-normal distribution of the outcome, confidence intervals and p-values will be obtained using a bias corrected and accelerated bootstrap resampling procedure with 10,000 replicates.					

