2.2 Schema

3 Study objectives and endpoints

The aims of the Randomized Trial of Telehealth vs. Conventional Hearing Care Delivery in the ACHIEVE Study (ACHIEVE Hearing Intervention Follow-Up, or ACHIEVE-HIFU) are:

Primary aims

1. To compare the effect of the telehealth HHC versus the conventional HHC delivery model on hours of hearing aid use (primary outcome) at 1 year post-randomization.

Secondary aims

- 2. To compare the effect of the telehealth HHC versus the conventional HHC delivery model on secondary outcomes of patient-centered hearing and communication outcomes, social functioning, and quality of life at 1 year post-randomization.
- 3. To compare utilization of hearing services required by each HHC delivery model.
- 4. To evaluate the association of the telehealth HHC intervention with changes in hearing aid use and patient-centered hearing and communication, social functioning, and quality of life measures from baseline to up to two years post-intervention.

Primary outcome

The primary outcome is average daily hours of hearing aid use obtained from objective hearing aid data logging at 1 year post-randomization. If a participant wears a hearing aid in both ears, then the ear with the greatest number of hours logged will be selected.

Secondary outcomes

- 1. Treatment satisfaction, as assessed by a single item from the International Outcome Inventory Comprehensive Hearing Intervention (IOI-CHI). The IOI-CHI is an interviewer-administered scale that consists of 6 items where participants self-report satisfaction with the hearing intervention using a 5-point Likert scale. A higher score indicates a more favorable outcome.
- 2. Ability to hear for the primary communication goal, as assessed by a single item from the Client-Oriented Scale of Improvement (COSI) goals achievement questionnaire. COSI goals are rated using a 5-point Likert scale. A higher score indicates the participant is able to hear more of the time.
- 3. Hearing-specific quality of life, as assessed by the Hearing Handicap Inventory for the Elderly Screening Version (HHIE-S) questionnaire. The HHIE-S is an interviewer-administered questionnaire that consists of 10 items. Participants rate whether hearing loss affects them in different situations (yes, sometimes, or no). The total score is the sum of all responses and ranges from 0 to 20, with higher scores indicating greater hearing issues.

Exploratory outcomes

Exploratory analyses may include, but are not limited to:

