- 8. Using mixed effects models to examine trends over time from randomization to the twoyear follow-up assessment. Time will be defined categorically or continuously with a time spline specified at 12 months. An interaction between treatment assignment and time will be included in the model to estimate the effect of participants in the conventional HHC treatment arm gaining access to telehealth services one-year postrandomization.

4 Background and rationale

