9.1 All participants

At the ACHIEVE trial year 3 visit, which will serve as the ACHIEVE-HIFU baseline visit, all participants will complete the hearing intervention check-up (see 7.2.1 above), and the audiologist will address any hearing aid maintenance or repairs, as needed.

At the ACHIEVE-HIFU randomization visit, after providing informed consent, participants will be randomized to receive either continued conventional clinic-based HHC or telehealth HHC delivery in addition to clinic-based care. All participants will complete the Telehealth Acceptance Pre-Intervention questionnaire before they will be given a GrandPad tablet with general instructions on how to set it up, an overview of its basic functionality, and how to access manufacturer support services. Prior to being informed of their randomized group, all participants will meet with the audiologist to complete COSI goal setting and complete the hearing intervention check-up (HICF). Participants will then be informed of their randomization assignments.

Participants randomized to the telehealth HHC delivery group will receive their first telehealth session at the end of the randomization visit, and they will continue to receive telehealth HHC for both years of the study, with clinic-based care occurring every 6 months. Participants randomized to the conventional clinic-based HHC delivery group will receive conventional clinic-based HHC for the first year of the study, receive their first telehealth session at the end of the Year 1 visit, and receive telehealth HHC for the second year of the study. The telehealth and conventional HHC delivery models are described next.

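### Both arms have telehealth after month 12, so the planned arm-by-time interaction gives the effect of late access only if the telehealth arm's own effect stays constant in year 2

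*SAP*

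**What the plan says.** SAP 7.6 item 8 plans mixed effects models from randomization to two years. On time coding it says: "Time will be defined categorically or continuously with a time spline specified at 12 months". It then adds an arm-by-time interaction, whose stated purpose is "to estimate the effect of participants in the conventional HHC treatment arm gaining access to telehealth services one-year post-randomization". Protocol section 3, exploratory outcome 8, has the same content ("An interaction between treatment assignment and time will be included in the model"). Neither document says which interaction coefficient or contrast will be reported.

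The treatment schedule is clear. For the telehealth arm, Protocol 2.1 says: "Participants randomized to the telehealth HHC group will receive telehealth HHC for both years of the study". Protocol 9.1 repeats it: "they will continue to receive telehealth HHC for both years of the study". For the other arm, Protocol 2.1 says: "In year two, participants randomized to continued conventional HHC will crossover to receive telehealth HHC". Protocol 9.3.1 and SAP section 4 agree.

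The item sits under a permissive lead-in, "Exploratory analyses may include, but are not limited to". The nearest protocol objective is secondary aim 4: "To evaluate the association of the telehealth HHC intervention with changes in hearing aid use and patient-centered hearing and communication". That aim speaks of association, whereas item 8 speaks of an effect.

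**The concern.** To estimate what the conventional arm gains from telehealth, one needs to know how it would have fared in year 2 without it. No concurrent group shows this, because the comparison arm is in its second year of telehealth. The interaction can stand in for the missing comparison only if the telehealth arm's effect neither wanes nor grows after month 12.

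If the effect wanes, the loss is credited to the conventional arm as a benefit of late access. If it keeps growing, the growth is deducted from that benefit. Waning is the more troubling case, because an intervention losing its effect would look like evidence that late access works. Item 8 is also the only two-year model that either document describes, so it is the likely source for any statement about secondary aim 4.

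**Working it through.** **No stated figure.** Item 8 gives no number, so there is nothing of the plan's own to reproduce. The check is algebra on arm means, followed by simulation.

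**Inputs.** The treatment schedule is from Protocol 2.1, 9.1 and 9.3.1 and SAP section 4. For scale only, SAP section 5 gives a detectable difference of 1.5 h and Protocol 11.1 gives 0.8 to 0.9 h. No document gives a year-2 change in the telehealth effect, so every value of E below is an assumption.

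**Definitions.** S1 and S2 are the changes in years 1 and 2 that both arms would show under conventional care. F is the telehealth arm's effect at month 12. E is the change in that effect during year 2. G is the conventional arm's true gain by month 24 from starting telehealth at month 12.

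| Mean relative to baseline | Month 0 | Month 12 | Month 24 |
|---|---|---|---|
| Telehealth arm | 0 | S1 + F | S1 + S2 + F + E |
| Conventional arm | 0 | S1 | S1 + S2 + G |

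**The 12-to-24-month interaction** (conventional minus telehealth), taken as a categorical contrast or as a separate year-2 slope:

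(S2 + G) - (S2 + E) = G - E

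Shared drift cancels, and E does not.

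| G assumed (h) | E assumed (h) | G - E (h) |
|---|---|---|
| 1.0 | 0 | 1.0 |
| 1.0 | -0.5 | 1.5 |
| 1.0 | +0.5 | 0.5 |
| 0 | -0.5 | 0.5 |
| 1.5 | -0.75 | 2.25 |
| 1.5 | +0.75 | 0.75 |
| 0.8 | -0.4 | 1.2 |
| 0.8 | +0.4 | 0.4 |

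Whenever E is half of G in size, the error is 50% of G in one direction or the other. The fourth row shows an apparent effect where there is none.

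**Other terms that the text permits.**

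- Linear time plus a hinge at 12 months: the arm-by-hinge term is the year-2 slope difference minus the year-1 slope difference. If the effect builds linearly over year 1, this is (G - E) - (-F) = G - E + F. With E = 0 and F = G it equals 2G.
- 24 months versus baseline: (S1 + S2 + G) - (S1 + S2 + F + E) = G - F - E. With E = 0 and F = G it equals 0.

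**Simulation.** Random-intercept mixed models were fitted to one simulated data set per scenario. Each had 3,400 people and visits at 0, 6, 12, 18 and 24 months, with true G = F = 1.5 h, drift of -0.5 h per year and effects linear within each year. Algebraic values are in brackets.

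| Telehealth effect in year 2 | Categorical, 24 minus 12 | Year-2 slope | Hinge term | 24 months vs baseline |
|---|---|---|---|---|
| Flat (E = 0) | 1.44 (1.50) | 1.47 (1.50) | 3.05 (3.00) | -0.14 (0) |
| Halves (E = -0.75) | 2.27 (2.25) | 2.27 (2.25) | 3.75 (3.75) | 0.77 (0.75) |
| Grows by half (E = +0.75) | 0.82 (0.75) | 0.82 (0.75) | 2.45 (2.25) | -0.78 (-0.75) |
| Grows as much again (E = +1.5) | 0.09 (0) | 0.08 (0) | 1.56 (1.50) | -1.39 (-1.50) |

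The largest departure from the algebra is 0.20 h (2.45 against 2.25), which is consistent with sampling error. For one true gain of 1.5 h and a flat year-2 effect, the permitted terms read about 1.5, 3.0 or 0.

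**The case against.** The strongest defence has four parts.

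1. The analysis is optional and exploratory. The primary and secondary comparisons are made at one year (SAP 7.3 and 7.5), and the multiplicity rule in SAP 7.7 does not cover item 8. This stands, and it limits the weight of the point.
2. Subtracting the telehealth arm's change is sound practice, because it removes shared drift in an ageing cohort. This also stands. A reader might infer that the subtraction is itself the mistake. It is not: the only bias in the 12-to-24-month contrast is E, and a plain before-after change in the conventional arm would be worse because it keeps the drift.
3. E may be zero. The three structured sessions fall within about six weeks (Protocol 9.2.1 and 9.2.2), and lighter contact continues afterwards (9.2.3). A plateau by month 12 fits this text, but so does waning or further growth. The documents do not choose, so the assumption has to be stated.
4. Item 8 is introduced as a look at trends, and secondary aim 4 claims only association. A reader might infer that the final report is bound to present a causal crossover effect. The documents do not commit to that, and they do not formally link item 8 to aim 4. What remains is the purpose clause itself, which calls the interaction an estimate of an effect.

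**Conclusion.** The point holds as a conditional one. Under the schedule in both documents, the 12-to-24-month interaction estimates G - E. It equals the effect of gaining access only if the telehealth effect is constant after month 12, and neither document states or defends that. Because coding and contrast are open, the text also permits terms with a different meaning: about 2G for the hinge term and about 0 for 24 months versus baseline. Both of those values assume a flat year-2 effect, linear build-up in year 1 and a late gain equal to the first-year effect.

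The size of any error is unknown. The 0.5 h and 50% figures follow from assumed values of E, so a reader who takes the estimate to be shown badly wrong goes further than the documents allow. The one-year primary comparison is unaffected. The change is still worth making, because following the text as written can attach the wrong number to the crossover.

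**What to change.** Amend SAP 7.6 item 8 and Protocol section 3, exploratory outcome 8, before the two-year data are analysed:

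- Fix the time coding and name the contrasts to be reported.
- Report (a) the arm difference at 24 months, described as immediate versus one-year-delayed access. Randomization supports this comparison. In the notation above it is G - F - E, so a value near zero can mean that the delayed arm caught up or that the telehealth arm lost its effect. It should be read together with (b).
- Report (b) each arm's 12-to-24-month change side by side, with their difference. Call that difference a between-arm difference in year-2 change. Call it the effect of gaining access only if the constant-effect assumption is written down and defended.
- Do not present the conventional arm's before-after change on its own as an effect.

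The cost is wording and two contrast statements from the same model. Protocol Table 1 already schedules 12- and 24-month measurement of the primary and all three secondary outcomes, so no new data are needed. The downside is a more modest claim about year 2.

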7.7 Adjustment for Multiple Comparisons

Statistical significance for the primary outcome will be defined as $p < 0.05$. Secondary outcomes will be evaluated for statistical significance with a Hochberg modification to the Bonferroni adjustment, in which the p-values of the five outcomes will be ordered. The largest p-value will be compared relative to $p < 0.05$,

and if met, all parameters will be considered significant. If not, then the second largest p-value will be assessed relative to $p < 0.05/2 = 0.025$, and if met then it and all other parameters will be considered significant, and so on for the third p-value at $0.05/3=0.017$.

8. Software and Statistical Programming

Tabulations and statistical analyses will be performed using SAS® Version 9 (or later). All programming will be done by the ACHIEVE DCC which is housed in the Collaborative Studies Coordinating Center (CSCC) at the University of North Carolina at Chapel Hill. Standard CSCC statistical computing procedures will be followed. That is, research staff will submit a written statistical computing request to the statistical programming staff. A computing request number will be assigned to the request and information about the request entered into a database. A statistical programmer will then be assigned to undertake the request. Statisticians will review the programs and output. If necessary, changes will be requested in writing. After the programming has been completed to the satisfaction of the staff, all materials will be archived under the request number. Archived materials will include the original computing request, any subsequent changes, the SAS® code as well as any output, including log and list files and datasets created in the request.

9. References

- [1] American Speech Language Hearing Association , "Preferred Practice Patterns for the Profession of Audiolog," *Rockville, MD*, 2006.
- [2] Audiology Australia, "Audiology Australia Professional Practice Standards – Part B: Clinical Standardsle," *Forest Hill, Victoria*, 2013.
- [3] British Society of Audiology, "Practice Guidance: Common Principles of Rehabilitation for Adults in Audiology Services," *Bathgate, UK*, 2016.
- [4] J. H.-Y. Ng and A. Y. Loke, "Determinants of hearing-aid adoption and use among the elderly: A systematic review," *Int J Audiol*, vol. doi: 10.3109/14992027.2014.966922, pp. 1-10, 2015; 2027 (April 2014).

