- 1. The 5 remaining items from the IOI-CHI, as well as a composite score created by computing the mean across all 6 items.
- 2. Ability to hear for the other two communication goals from the COSI goals achievement questionnaire, as well as a composite score created by computing the mean across all 3 goals.
- 3. Telehealth acceptance, as assessed by an interviewer-administered scale that consists of 5 items in which participants rate the ease of use or utility of telehealth equipment using a 5-point Likert scale. A higher score indicates a more favorable rating. Each item will be examined separately before being analyzed collectively as part of a composite score created by computing the mean across all 5 items.
- 4. Subgroup analyses of the primary and secondary outcomes including, but not limited to, sex, race, and education. Interactions between treatment assignment and subgroups will be tested relative to p < 0.10.
- 5. The effect of treatment assignment on the total number of contacts between the provider and participant. The total number of provider-participant contacts is quantified by the study audiologists using forms completed at every encounter. In a supplemental analysis, the number of contacts will be examined across specific modalities, including face-to-face contact in a clinic, face-to-face contact outside of a clinic (e.g., home visits), and remote contact (e.g., video calls, phone calls, etc.).
- 6. The effect of treatment assignment on the total time spent between the provider and participant. The total number of minutes during which the provider and participant

- interacted is quantified by the study audiologists using forms completed at every encounter. In a supplemental analysis, the number of minutes will be examined across specific modalities, including face-to-face contact in a clinic, face-to-face contact outside of a clinic, and remote contact.
- 7. Estimating the linear and potentially nonlinear dose-response relationship between utilization of hearing services and hours of hearing aid use at one-year post-randomization. This will include testing the total number of contacts between the provider and participant, the total amount of time the provider and the participant spend interacting, and differences by modalities such as face-to-face contact in a clinic, face-to-face contact outside of a clinic, and remote contact.

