7.7 Dementia and MCI assessments

A syndromic diagnosis of MCI and dementia will be determined and used as secondary outcomes. Current criteria for MCI³⁵ and dementia,³⁶ which prominently included investigators for this project, are now well-established and have been employed successfully in ARIC-NCS and ACHIEVE. Details of the diagnostic procedures and normative data have been published and are enumerated in the Manual of Procedures. Briefly, MCI and dementia syndromic

diagnoses are determined by a panel of clinicians, taking into account performance on the neuropsychological battery (test scores are compared to age, education, and race-specific norms), cognitive decline across study visits, and subject and informant interviews regarding cognitive functional status. Based on these elements, all examined participants have a computer-algorithmic classification followed by expert-adjudicated review. The computer algorithm, also developed by the expert panel for ARIC-NCS, has been used successfully to enhance uniformity in applying the diagnostic criteria. In ARIC-NCS, the computer algorithm-reviewer agreement was high: 99% for normal, 94% for MCI, and 95% for dementia, suggesting that the algorithm accords well with clinical judgment. The informant interviews noted above are conducted with a knowledgeable informant at every exam where the participants meet a priori criteria for poor cognitive performance and who have significant cognitive decline from prior exams.

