7.5 Secondary Outcomes

Secondary outcomes that will be examined include:

1. Treatment satisfaction, as assessed by a single item from the International Outcome Inventory – Comprehensive Hearing Intervention (IOI-CHI). The IOI-CHI is an interviewer-administered scale that consists of 6 items where participants self-report satisfaction with the hearing intervention using a 5-point Likert scale. A higher score indicates a more favorable outcome.
2. Ability to hear for the primary communication goal as assessed by a single item from the Client-Oriented Scale of Improvement (COSI) goals achievement questionnaire. COSI goals are rated using a 5-point Likert scale. A higher score indicates the participant is able to hear more of the time.
3. Hearing-specific quality of life, as assessed by the Hearing Handicap Inventory for the Elderly Screening Version (HHIE-S) questionnaire. The HHIE-S is an interviewer administered questionnaire that consists of 10 items. Participants rate whether hearing loss affects them in

different situations (yes, sometimes, or no). The total score is the sum of all responses and ranges from 0 to 40, with higher scores indicating greater hearing issues.

For continuous secondary outcomes, groups will be compared for differences at the one-year follow-up using the same analytic approach specified for the primary outcome. For binary secondary outcomes, either logistic regression or Poisson regression with robust error variance will be employed depending on whether the outcome is rare or common. For categorical outcomes, either ordinal or multinomial logistic regression models will be utilized depending on the nature of the measure and empirical tests of the proportional odds assumption.

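### The Hochberg rule counts five secondary outcomes, but both documents list three and print only the cut-offs for three, so the family size is unsettled

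*SAP*

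**What the plan says.** SAP 7.7 tests the primary outcome on its own at p < 0.05 and applies a Hochberg procedure to the secondary outcomes, "in which the p-values of the five outcomes will be ordered". The largest p-value is compared with 0.05, the second largest with 0.05/2 = 0.025 and the third with 0.05/3, printed as 0.017. No further cut-off is given. The step after the first reads "and if met then it and all other parameters will be considered significant, and so on for the third p-value". Protocol 11.2 has essentially the same paragraph, including the number five.

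The outcome lists give a different count:

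- SAP 7.5 opens with "Secondary outcomes that will be examined include" and numbers three: the IOI-CHI satisfaction item, the COSI item for the primary communication goal, and the HHIE-S.
- Protocol section 3 numbers the same three.
- The Protocol synopsis (2.1) gives the same three as key secondary outcomes, ending with "Hearing-specific quality of life, as assessed by the Hearing Handicap Inventory for the Elderly Screening Version (HHIE-S) questionnaire".

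The leftover items of the first two instruments are placed elsewhere. Protocol section 3 puts "The 5 remaining items from the IOI-CHI, as well as a composite score" under exploratory outcomes, and SAP 7.6 does the same with "The 2 remaining items from the COSI as well as a composite score".

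One Protocol sentence stands apart from the lists. Section 7.7 says of cognitive diagnoses: "A syndromic diagnosis of MCI and dementia will be determined and used as secondary outcomes".

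**The concern.** The paragraph in SAP 7.7 and Protocol 11.2 is the decision rule for every secondary claim, and its stated family size does not match the outcomes listed for it. The two documents repeat the same figure, so neither corrects the other.

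A reader who trusts the lists tests three outcomes. A reader who trusts the number must find two more, and the documents do not say which. If that is settled after results are known, the choice can change which secondary results are declared significant. SAP 7.1 allows the plan to be modified during analysis where deviations make the proposed analyses inappropriate, so the text should leave no such choice open.

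**Working it through.** **Inputs.** Alpha 0.05, the Hochberg method, the cut-offs 0.05, 0.025 and 0.017, and the number five come from SAP 7.7 and Protocol 11.2. The three outcomes come from SAP 7.5 and Protocol 2.1 and 3. The p-values, effect sizes and correlations below are assumptions, because the documents give none.

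**Reproducing the cut-offs.** Hochberg compares the k-th largest p-value with 0.05/k, for k = 1 to m.

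| k | 0.05/k | Printed in the plan | Needed for m = 3 | Needed for m = 5 |
|---|---|---|---|---|
| 1 | 0.05 | yes | yes | yes |
| 2 | 0.025 | yes | yes | yes |
| 3 | 0.0167 | yes, as 0.017 | yes | yes |
| 4 | 0.0125 | no | no | yes |
| 5 | 0.01 | no | no | yes |

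The printed set is complete for three tests and stops two short for five.

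**Effect on verdicts.** The rule was applied to two illustrative sets of p-values for the listed outcomes, first alone and then with two added outcomes.

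| Listed p-values | m = 3 | m = 5, extras 0.40 and 0.60 | m = 5, extras 0.001 and 0.002 |
|---|---|---|---|
| 0.015, 0.20, 0.30 | 1 significant | 0 of the listed | 1 of the listed |
| 0.02, 0.03, 0.04 | 3 significant | 0 of the listed | 3 of the listed |

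In the second row with m = 3, the largest value, 0.04, is below 0.05, so all three pass. With extras 0.40 and 0.60, those two fail at 0.05 and 0.025. The listed values then meet smaller cut-offs and fail in turn: 0.04 against 0.0167, 0.03 against 0.0125, 0.02 against 0.01.

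**Direction.** Cut-offs count down from the largest p-value. An added outcome can leave a listed one at the same cut-off or push it to a smaller one, but can never give it a larger one. In 300,000 random sets of five p-values, enlarging the family from three to five never added a significant result among the first three.

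**Power.** Assume independent tests, 80% power for each real effect tested alone at two-sided 0.05, and two extra outcomes with no effect. Power for a listed outcome by simulation:

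| Listed outcomes with an effect | m = 3 | m = 5, all five cut-offs | Five p-values, only the three printed cut-offs |
|---|---|---|---|
| One | 66% | 59% | 0.1% |
| All three | 76% | 64% | 30% |

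The last column is the literal text: five p-values ordered, with testing ending at the third.

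**Error control for three outcomes.** For independent tests under the full null, no rejection occurs when all p-values are at least 0.05/3, at most one is below 0.025, and at least one is 0.05 or more. The width from 0.05/3 to 0.025 is 0.00833.

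- P(no rejection) = (0.975³ − 0.025³) + 3 × 0.00833 × (0.975² − 0.025²) = 0.92684 + 0.02375 = 0.95059, so familywise error is 4.9%.
- Simulation with equally correlated normal tests gives 4.8% at correlation 0.3, 4.6% at 0.5 and 3.8% at 0.8.
- With the rounded 0.017, the second term becomes 3 × 0.008 × 0.95 = 0.0228, and the error is 1 − 0.94964 = 5.04%. That is trivial, but it is a reason to state 0.05/3 unrounded.

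**The case against.** The strongest reply is that the slip has no effect on the obvious reading. The first three Hochberg cut-offs do not depend on family size, so an analyst who tests the three listed outcomes reaches the same verdicts whether the text says three or five. Familywise error is controlled, and moving to five later cannot rescue a listed outcome that failed. All of this is correct. It means verdicts change only if two further outcomes enter the family, and then only towards fewer significant results among the three. The examples above are illustrations, not forecasts.

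A second reply is that five may be intended. The Protocol offers routes to it: MCI and dementia (section 7.7), or contacts and contact time as two measures of service utilization, which is a secondary aim. Secondary aim 2 also mentions social functioning, which none of the three listed outcomes measures. However, both documents class the utilization measures as exploratory, and no text places these or the cognitive diagnoses in the Hochberg family. The routes do not establish five. They do show that a reader who takes the number at face value has more than one way to fill the two places, so the text does need to settle it.

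**Conclusion.** The concern holds. The count in the rule conflicts with every secondary outcome list and with the rule's own cut-offs, and a five-member procedure cannot be run in full from the text. Three is the best-supported family size, although the documents do not state it.

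The consequence is confined to secondary claims and depends on two unnamed outcomes being added. In that case the cut-off for the smallest p-value falls from 0.0167 to 0.010, and power for a listed outcome falls by about 7 to 13 percentage points under the stated assumptions (66.2% to 59.1%, and 76.5% to 63.5%). Error control for three outcomes is sound, and the primary test is untouched. This should be fixed, but it does not threaten the trial's main conclusion.

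Two lesser points do not carry the finding. Read literally, the step after a failed largest p-value would also declare that failed outcome significant, although the named method makes the intent fairly clear. The secondary label for MCI and dementia in Protocol 7.7 conflicts with the outcome lists.

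**What to change.** Amend SAP 7.7 and Protocol 11.2 together, before the unblinding described in SAP 7.1, in one of two ways:

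- change five to three and name the family as the IOI-CHI satisfaction item, the COSI primary goal item and the HHIE-S; or
- if five is intended, list all five in the secondary outcome sections and add the cut-offs 0.0125 and 0.01.

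In either case, give the third cut-off as 0.05/3, and say that once a p-value meets its cut-off, that outcome and all outcomes with smaller p-values are significant. Reconcile the sentence on MCI and dementia in Protocol 7.7 with the outcome lists.

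The cost is a few words in one paragraph of each document and one sentence in Protocol 7.7; the second option also needs the added outcomes in the lists. Saying three changes neither data collection nor the primary analysis.
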